## **Multicenter studies** 4.4

All centers will be pooled and no analysis by center will be performed.

## 4.5 Multiple comparisons/multiplicity

There will be no formal hypothesis testing in this study; therefore, adjustments for multiplicity are not required.

## 4.6 Use of an efficacy subset of study participants

No efficacy subset will be defined for this study.

#### 5 STUDY POPULATION CHARACTERISTICS

## 5.1 Study participant disposition

The number of screened study participants, and reasons for screen failure, will be summarized for all screened study participants.

The number and percentage of study participants who were treated, and who discontinued from the study, along with the discontinuation reasons, will be summarized for the Safety Set by CZP Dose (Reduced, Original and Any) and Baseline weight group as well as by CZP Dose and ADAb titer classification; because the study was closed, every ongoing study participant is discontinued from the study. For the Week 16, the number of study participants completing Week 16 was added. For the Updated Week 24 Interim Analysis, the number of study participants completing Week 24 was added. For the Final Analysis, the number of study participants completing Week 24 and Week 48, respectively, will be added. The disposition of study participants in their initial dosing phase, reduction phase and escalation dosing phase of the study will also be presented. The number of study participants in each analysis set will be presented.

Discontinuations due to AEs will be summarized separately for the SS, and will be provided for the Reduced CZP Dose, Original CZP Dose, and Any CZP Dose groups.

The number and percentages of study participants impacted by COVID-19 will be presented for overall and by impact visit, for any reason for all study participants in the SS. This data will be presented in study participant data listings.

Study participant disposition details will be listed, along with a listing of visit dates per study participant. A listing of analysis sets per study participant will also be presented.

## Protocol deviations 5.2

The number and percentage of study participants with important protocol deviations will be summarized by type for the SS for the Reduced CZP Dose, Original CZP Dose, and Any CZP Dose. All important protocol deviations will also be listed.

Note that PK sample exclusion will be implemented due to certain protocol deviations; see Section 3.5. Study participants with at least one PK data exclusion from scheduled visits are summarized and listed.

## **DEMOGRAPHICS AND OTHER BASELINE** 6 **CHARACTERISTICS**

All summaries of demographics and Baseline characteristics will be provided for the SS; selected summaries as specified below will also be summarized for the PK-PP set.

## 6.1 **Demographics**

Demographics will be summarized for the SS and the PK-PP Set for the Reduced CZP Dose, Original CZP Dose, and Any CZP Dose groups. The following continuous variables will be summarized by Baseline weight group and ADAb titer classification: age (years), weight (kg), height (cm), body surface area (BSA) and body mass index (BMI) (kg/m^2) at Baseline.

Confidential Page 39 of 252 The following categorical variables will be summarized by Baseline weight group and ADAb titer classification: gender (male, female), racial group (American Indian/Alaskan Native,

Other baseline characteristics

Baseline characteristics described in this section will be summarized for the SS and the PK-PP Set for the Reduced CZP Dose, Original CZP Dose, and Any CZP Dose groups. Time since first diagnosis of pcJIA (or onset of signs and symptoms consistent with pcJIA for those enrolled after Protocol Amendment 3) will be calculated as the duration from the dot [Visit2]); time since diagnosis and positions are since first diagnosis. e of cach of a each of a each of a each of will h number and percentage of study participants with a history of each of the following pcJIA categories will also be summarized:

- Polyarthritis rheumatoid factor-positive
- Polyarthritis rheumatoid factor-negative
- Extended oligoarthritis
- Juvenile psoriatic arthritis
- Enthesitis-related arthritis

Other baseline characteristics information will be listed.

## Medical history and concomitant diseases

Medical history excluding pcJIA will be summarized by MedDRA® System Organ Class (SOC) and Preferred Term (PT) for Reduced CZP Dose, Original CZP Dose, and Any CZP Dose, and will include the number and percentage of study participants with each PT present. Medical history, JIA history and a glossary of medical history conditions will be listed.

### Prior and concomitant medications 6.4

Prior medications include any medications that started prior to the start date of study medication, and also include any medications that continue post-Baseline. Past medications are a subset of prior medications and include prior medications with a stop date before the date of first study medication administration. Concomitant medications are medications taken at least one day in common with the study medication dosing period. For Cimzia, the dosing period is from the date of first dose up to (but not including) 14 days Q2W (or 28 days if (04W) post last dose if a study participant discontinued early or at end of treatment per protocol. For ongoing study participants, the dosing period is from the date of first dose up to the data cutoff date in interim analyses. Thus a concomitant medication is any medication whose start date is prior to the date of last study medication administration + 14 days Q2W

(or +28 days if Q4W) or data cutoff date, and whose stop date is either missing, or on or after the date of first study medication administration.

All prior medications will be summarized by anatomical therapeutic chemical (ATC) classification level 3 (Pharmacological Subgroup) and WHO-DD generic name. The number of DMARDs stopped prior to Baseline and not re-initiated during the study will be assessed and summarized. For those study participants with these stopped DMARDs, the WHO-DD generic name will be summarized. These summaries will be provided for the SS for the Reduced CZP Dose, the Original CZP Dose and the Any CZP Dose.

Concomitant medications will be summarized for all medications, and separately for DMARDs, systemic corticosteroids, and intra-articular corticosteroid injections. DMARDs and corticosteroids will be identified through ATC codes and medical review. Concomitant medications will be summarized by ATC level 3 and WHO-DD generic name. All summaries of concomitant medications will be provided for the SS for the Reduced CZP Dose, Original CZP Dose, and Any CZP Dose groups.

Listings of all prior and concomitant medications will be provided as well as a glossary of the concomitant medications.

Medications related to triamcinolone with the following WHO-DD generic names will be grouped and appear in summaries as "Triamcinolone" with the ATC3 level label of "UCB Triamcinolone ATC3": triamcinolone, triamcinolone acetonide, triamcinolone hexacetonide, triamcinolone acetate, triamcinolone acetonide dipotassium phosphate.

Medications related to prednisone with the following WHO-DD generic names will be grouped and appear in summaries as "Prednisone" with the ATC3 level label of "UCB Prednisone ATC3": prednisone, prednisolone, prednisolone acetate, prednisolone sodium phosphate, methylprednisolone, methylprednisolone acetate.

Medications related methotrexate with the following WHO-DD generic names will be grouped and appear in summaries as "Methotrexate" with the ATC3 level label of "UCB Methotrexate ATC3": methotrexate, methotrexate sodium.

## 6.5 Prohibited medications

The following medications are prohibited at any time during the study:

- Nonbiologic DMARDs (other than MTX) and biologic DMARDs (eg, anakinra, rilonacept, etanercept, adalimumab, infliximab, golimumab, rituximab, abatacept, tocilizumab, CZP other than study medication).
- Any experimental (biological or non-biological) therapy (within or outside a clinical study).
  Live and live attenuated vaccineties.
  - Live and live attenuated vaccinations including, but not limited to, oral polio, chicken pox (varicella), measles-mumps-rubella (MMR), nasal influenza, and rotavirus. No data are available on the response to live vaccinations or the secondary transmission of infection by live vaccines in study participants receiving CZP.

All efficacy data collected at any assessments after the use of prohibited medications that could impact efficacy will be treated as non-response for binary endpoints in all analyses The +1 day rule was applied to the first usage date when considering its impact on efficacy endpoints. Therefore, only efficacy data with dates after the first usage date of the prohibited medication were impacted (using the non-responder imputation (NRI) method).

All summaries of prohibited medications will be provided for the CC ?

Dose, the Original CZP Dose and the Any CZP ?

listed.

#### 6.6 **Rescue medications**

Rescue medication use is defined as any initiation of treatment or increase in dose of a medication used to treat pcJIA (in addition to the study drug) that is considered to impact the efficacy analyses. In general, a study participant requiring rescue medication after first administration of study drug is considered as a treatment failure from that time point forward for the purpose of efficacy analyses. Use of some short-acting medications (detailed below) may result in efficacy data at the next scheduled visit being treated as non-response (for categorical data).

A study participant requiring rescue medication may remain on study medication if the benefit/risk assessment of the study participant's continued participation is still favorable based on the Investigator's clinical assessment.

The use of rescue medication should be specifically avoided during the first 4 months (16 weeks) of treatment, if possible.

The following medications are defined as rescue medication in the first 16 weeks of this study:

- Initiation of MTX (if not being used at study entry), or increase of MTX above Baseline.
- Initiation of oral corticosteroids, or increase of oral corticosteroids above Baseline.

The following medications are defined as rescue medication when initiated in the first 56 weeks of the study:

- Initiation of MTX (if not being used at study entry), and increase of MTX above 15mg/m^2 per week at any time (based upon study participant's most recent body surface area [BSA] prior to an increase in MTX).
  - Initiation of oral corticosteroids, or increase to >10mg or 0.2mg/kg prednisone (or equivalent) per day (whichever is the smaller dose). A study participant's most recent weight prior to an increase of oral corticosteroids will be used to determine if the dosage increase meets the criterion.

BSA will be calculated using Mosteller's formula (Mosteller, 1987):

BSA (m^2) = 
$$\sqrt{\frac{\text{height (cm)} \times \text{weight (kg)}}{3600}}$$

The following medications are defined as rescue medication when initiated at any time up to Week 56 during the study:

- Injection of intra-articular (ia) corticosteroids into more than 2 joints at a single time point.
- Injection of intra-articular (ia) corticosteroids into the same joint more frequently than 3 times in a 12-month (365 day) period. When such cases occur, the fourth injection within 12 months will be considered the time point at which rescue medication was initiated for the study participant.
- Intravenous (iv) corticosteroids (any dose), if not used for stress dosing for the purposes of surgery.
- Intramuscular (im) corticosteroids.

Any joint injected with ia corticosteroids will be excluded from the efficacy analysis for a period of 3 months (91 days).

In all cases, any medications recorded in the database will be classified as rescue medication only when pcJIA is listed as the indication for that medication. Rescue medication use and date of first usage will be confirmed during the data cleaning meetings prior to the database lock. Generally, the +1 day rule was applied to the first usage date when considering its impact on efficacy endpoints. Therefore, only efficacy data with dates after the first usage date of the rescue medication were impacted (using the non-responder imputation (NRI) method). The number and percentage of study participants who used rescue medication up to the Week 16 visit and after the Week 16 visit will be summarized separately.

All summaries of rescue medications will be provided for the SS for the Reduced CZP Dose, the Original CZP Dose and the Any CZP Dose. All rescue medication will be listed.

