#### 2.2.2 Secondary variables

Efficacy will be assessed by the PedACR30, PedACR50, PedACR70 and PedACR90 response rates at Week 16 as compared to Baseline.

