## 4.2 Handling of dropouts or missing data

For all binary efficacy endpoints assessing response (PedACR30, PedACR50, PedACR70, PedACR90, CID, CRM), a study participant having missing data for the time point assessed will be conservatively counted as a non-remitter or non-responder. This will be done whether the data is missing, the study participant discontinued the study prior to the time point assessed, or the data is considered missing due to use of prohibited or rescue medication.

For all non-missed visits, if any of the PedACR core set measures are missing then those scores will be considered as not having met the criteria for improvement in the PedACR30, PedACR50, PedACR50, PedACR50 and PedACR90 response analyses. PedACR30, PedACR50, PedACR50, and PedACR90 responses will be derived if a single core set measure is missing. However, if 2 or more core set measures are missing, the corresponding PedACR30, PedACR50, PedACR50 and PedACR90 responses will in general be treated as missing.

Derived binary efficacy endpoints at visits affected by the use of rescue medications, or prohibited medications, will be treated as non-response. See Section 6.7 for a list of medications which would result in all efficacy data at only the next scheduled visit (and not all subsequent visits) being treated as missing/non-response. Any joint receiving intra-articular corticosteroids will be treated as missing with respect to assessments of that joint for 3 months (91 days).

For continuous efficacy endpoints, missing assessments will not be imputed.

For the non-responder imputation (NRI) calculations for binary efficacy outcomes,

- the study participants who discontinued up to and including Week 56, NRI will be imputed up to Week 56,
- the study participants who discontinued after Week 56, no imputation will be performed after the last visit,
- for study participants who take rescue and prohibited medications (see Section 6.6),
  - for visits up to and including Week 56, the outcomes are imputed as NRI up to Week
     56
  - for visits after Week 56, the outcomes are imputed as NRI if medication initiation is before or on Week 56
- for the initiation of rescue, short-acting or prohibited medications after Week 56, then the NRI imputation is not applied.

No further imputations of any other missing data are planned (eg, efficacy data missing at random).

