## 6.7 Short-acting medications

Use of the following medications, which are not rescue medications, only results in efficacy data at the next scheduled visit being treated as missing/non-response:

- Higher than Baseline dose of nonsteroidal anti-inflammatory drugs (NSAIDs) and cyclooxygenase-2 (COX-2) inhibitors, including as needed (PRN) use within 72 hours prior to scheduled study visit (Note: No intake at baseline is considered equivalent to a baseline dose of 0).
  - Higher than Baseline dose of analgesics or opioids including PRN use within 48 hours prior to scheduled study visit (Note: No intake at baseline is considered equivalent to a baseline dose of 0).
- Any increase in dose of oral corticosteroids within 7 days prior to scheduled study visit (Note: The increase has to be higher than baseline).

Confidential

All medication data resulting in efficacy data being treated as missing/non-response will be flagged in the concomitant medication listing.

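### For a pcJIA-indicated oral corticosteroid increase in the 7 days before a visit in the first 16 weeks, SAP 6.6 says rescue with lasting non-response and SAP 6.7 says not rescue with non-response at one visit, and no rule says which prevails

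*SAP*

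**What the plan says.** Section 6.6 opens one of its lists with "The following medications are defined as rescue medication in the first 16 weeks of this study". The corticosteroid item there is "Initiation of oral corticosteroids, or increase of oral corticosteroids above Baseline", with no dose threshold and no exception for timing relative to a visit. A participant who needs rescue is, in general, "considered as a treatment failure from that time point forward for the purpose of efficacy analyses". Section 6.6 also limits rescue to medication whose listed indication is pcJIA. A second list, for initiation in the first 56 weeks, covers starting oral corticosteroids or raising them above 10 mg or 0.2 mg/kg prednisone equivalent per day, whichever is smaller.

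Section 4.2 imposes non-response after rescue at visits up to Week 56. For later visits, "the outcomes are imputed as NRI if medication initiation is before or on Week 56".

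Section 6.7 states: "Use of the following medications, which are not rescue medications, only results in efficacy data at the next scheduled visit being treated as missing/non-response". Its third item is "Any increase in dose of oral corticosteroids within 7 days prior to scheduled study visit", with a note that the increase must exceed the Baseline dose. It sets no limit by study week, dose or indication. Section 4.2 points to this list as affecting data "at only the next scheduled visit (and not all subsequent visits) being treated as missing/non-response".

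Two outputs depend on the classification. One is the secondary efficacy variable in Section 2.2.2, PedACR30, PedACR50, "PedACR70 and PedACR90 response rates at Week 16 as compared to Baseline". The other is the Section 6.6 summary of rescue use, split at the Week 16 visit.

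**The concern.** One event fits two definitions with opposite labels and different consequences. Take a child whose prednisone is raised for pcJIA from 2.5 to 5 mg/day four days before the Week 12 visit. Section 6.6 makes this rescue: the child is a non-responder at Week 12 and at every later visit, and enters the rescue count. Section 6.7 makes it not rescue: Week 12 is lost, Week 16 is taken as observed, and the child is not in the rescue count.

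The discrepancy has one direction. Following Section 6.7 can only leave the response rate equal or higher and the rescue rate equal or lower. It also produces an odd ordering, because an increase three days before a visit would be treated more mildly than the same increase eight days before it. Two competent programmers could each follow the text and report different Week 16 response rates and rescue counts.

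**Working it through.** **Inputs.** The rules are in SAP Sections 4.2, 6.6 and 6.7. The visit schedule is in Table 2-2: Weeks 4, 8, 12, 16, 20, 24, 32 and every 8 weeks thereafter. Group sizes come from Section 2.3 (163 participants in the 24-week interim) and Section 2.4 (78 enrolled on the Original Dose, 30 added under Protocol Amendment 9).

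**Step 1. Apply both rules to one event.** The event is a pcJIA-indicated increase above Baseline in the 7 days before the visit shown, in a participant with no other rescue use.

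| Increase precedes | Week 16 under 6.6/4.2 | Week 16 under 6.7 | Week 16 rule differs? | Rescue count up to Week 16 (6.6 / 6.7) |
|---|---|---|---|---|
| Week 4 | non-response | as observed | yes | 1 / 0 |
| Week 8 | non-response | as observed | yes | 1 / 0 |
| Week 12 | non-response | as observed | yes | 1 / 0 |
| Week 16 | non-response | non-response | no | 1 / 0 |

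The rescue count differs in all four rows. Week 16 PedACR differs only in the first three, and then only if the observed Week 16 result is a response. In the last row, responses from Week 20 onward can still differ.

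**Step 2. Visits affected in the example.** Under 6.6/4.2, the non-response visits from Week 12 to Week 56 are 12, 16, 20, 24, 32, 40, 48 and 56, which is 8 visits, plus all visits after Week 56. Under 6.7 it is 1 visit.

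**Step 3. Weeks 16 to 56.** An increase is then rescue only above the 10 mg or 0.2 mg/kg threshold, so the overlap is limited to those increases and to initiation, if initiation counts as an increase from zero.

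**Step 4. Group sizes.** Reduced: 163 − 78 = 85. Original: 78 + 30 = 108. Any: 85 + 108 = 193. The split of the 163 reproduces the Week 12 rates in Section 2.3:

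- PedACR30: 59/78 = 75.6%, 67/85 = 78.8%, 126/163 = 77.3%.
- PedACR50: 50/78 = 64.1%, 60/85 = 70.6%, 110/163 = 67.5%.

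**Step 5. Shift per reclassified responder.** The shift is 100 × 1/n points:

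- Reduced: 100/85 = 1.2.
- Original: 100/108 = 0.9.
- Any: 100/193 = 0.5.

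The number of such participants is not in the SAP, so the calculation stops here.

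**The case against.** The best defence is that the sections can be read together. Section 6.6 defines rescue by drug, dose, period and indication, and Section 6.7 covers what is left over. On that reading the third item of 6.7 still has work to do: increases for other illnesses at any time, and pcJIA increases below the threshold after Week 16. The rival reading penalises an increase less the closer it falls to a visit, which is a reason to doubt that it was meant. Rescue use and its first date are also confirmed at data cleaning meetings before database lock.

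Much of this stands. The residual reading is the sensible one and probably the intended one. But the text does not state it. Section 6.7 says flatly that its medications are not rescue, without excepting those that meet 6.6. Section 6.6 calls its failure rule general and then introduces the next-visit effect of short-acting medications, so 6.7 can fairly be taken as a specific exception. The data cleaning meetings confirm cases but supply no rule.

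Three stronger inferences are not supported:

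- That every above-Baseline increase in the first 16 weeks is rescue. The pcJIA indication requirement excludes increases given for other reasons.
- That the Week 16 rates shift by some stated number of points overall. That needs a frequency, and the SAP gives none.
- That a formal conclusion is at risk. Section 10.1 names no primary efficacy variable, Sections 3.1 and 4.5 rule out hypothesis testing, and Section 4.3 records that the Week 16 futility check has been passed.

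**Conclusion.** The contradiction is in the current text and is minor. It concerns oral corticosteroid increases above Baseline, indicated for pcJIA, in the 7 days before a scheduled visit in the first 16 weeks. Between Weeks 16 and 56 it is narrower, as shown in the working.

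The supported size is the per-participant shift in Step 5. It assumes that the planned 30 were enrolled on the Original Dose and that all participants count in the Week 16 denominator; exclusions from the Full Analysis Set would make each shift slightly larger. A descriptive secondary result and a rescue summary are affected. The point is still worth settling, because the final analysis runs under this SAP and the ambiguity can only flatter the result.

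**What to change.** Add a clause to the third item of Section 6.7 so that it applies only to an increase that does not meet a rescue criterion in Section 6.6, including the pcJIA indication requirement. Section 6.6 then takes precedence. Section 6.7 keeps increases for other indications and, after Week 16, pcJIA increases below the threshold.

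The cost is one clause and a check of the derivation flag that separates rescue from short-acting use. No new data are needed. Tables are re-run only if the program followed Section 6.7 where both rules apply.
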